8.6.2 Statistical Methods for Safety Analyses

Safety and tolerability will be assessed by clinical review of all relevant parameters including adverse experiences and laboratory parameters. The primary safety analysis will summarize the safety data for subjects during the treatment period plus 14 days of follow-up. The 95% CIs for the safety parameters will be estimated using the Clopper-Pearson method [49], which is a conservative exact method of providing CIs in this estimation study.

The analysis of safety parameters will follow a tiered approach (Table 17). The tiers differ with respect to the analyses that will be performed.

The first tier includes the following safety parameters or adverse experiences of special interest that will be assessed via point estimates with 95% confidence intervals for each treatment arm for GT1, GT2, GT3, GT4, GT5 and GT6 subjects and combined across genotypes after 12 weeks of treatment: (1) AEs of elevated laboratory values that are reported as ECIs described in Section 7.2.3.2; (2) at least one AE; (3) a drug-related AE; (4) an SAE; (5) a serious and drug-related AE, and (6) an AE leading to discontinuation.

All other safety parameters will be included in the second tier with point estimates to be provided for each treatment arm for GT1, GT2, GT3, GT4, GT5 and GT6 subjects and combined across genotypes after 12 weeks of treatment for the following safety parameters: specific AEs by System Organ Class (SOC), vital signs, 12-lead ECGs, and standard laboratory safety tests at time points specified in the Trial Flow Chart (Section 6.0).

Missing safety laboratory, vital signs, or ECG values will be handled using the Data-As-Observed (DAO) approach, that is, any missing value will be excluded from the analysis. The only exception is when a Baseline/Day 1 result is missing, this will be replaced with the latest pre-treatment result, if available.

Table 17 Analysis Strategy for Safety Parameters

Safety Endpoint [†]	95% CI	Descriptive Statistics
AEs of elevated laboratory values that are reported as ECIs	X	X
Any AE	X	X
Any SAE	X	X
Any Drug-Related AE	X	X
Any Serious and Drug-Related AE	X	X
Discontinuation due to AE	X	X
Specific AEs, SOCs or PDLCs		X
Change from Baseline Results (laboratory, vital signs, ECG)		X
[†] Adverse Experience references refer to both Clinical and Laboratory AEs. Note: SOC=System Organ Class; PDLC=Pre-Defined Limit of Change; X = results will be provided.		

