7.1.5.3 Treatment Period

Treatment Day 1 (Visit 2)

Subjects should fast overnight prior to reporting to the study site for dosing on Treatment Day 1 (Visit 2).

Pre- and Post-Treatment Procedures

Day 1 procedures listed on the Study Flow Chart should be performed prior to dosing unless specified otherwise. For female subjects, a urine pregnancy test will be performed at the site prior to study drug initiation. If the urine pregnancy test result is negative, the subject will be eligible for allocation and the remainder of the pretreatment (Day 1) testing/procedures will be performed. If the urine pregnancy test result is positive, a serum pregnancy test will be performed. If the result of the serum pregnancy test is positive, the subject must not be randomized or allocated to treatment in the study.

Blood and urine will be collected for assay of safety evaluations, plasma HCV RNA, plasma HIV RNA, and PK measurements. These samples will be sent to the appropriate central laboratory(ies) following the procedure(s) set forth in the manual(s).

Additional samples will be collected for genetic evaluation of host parameters related to the response of HCV subjects to MK-3682 and MK-8408.

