7.2.3.2 Events of Clinical Interest

Selected non-serious and serious adverse events are also known as Events of Clinical Interest (ECI) and must be reported to the Sponsor.

For the time period beginning when the consent form is signed until treatment allocation/randomization, any ECI, or follow up to an ECI, that occurs to any subject must be reported within 24 hours to the Sponsor if it causes the subject to be excluded from the trial, or is the result of a protocol-specified intervention, including but not limited to washout or discontinuation of usual therapy, diet, placebo treatment or a procedure.

For the time period beginning at treatment allocation/randomization through 14 days following cessation of treatment, any ECI, or follow up to an ECI, whether or not related to the Sponsor's product, must be reported within 24 hours to the Sponsor, either by electronic media or paper. Electronic reporting procedures can be found in the EDC data entry guidelines. Paper reporting procedures can be found in the Investigator Trial File Binder (or equivalent).

Events of clinical interest for this trial include:

1. an overdose of Sponsor's product, as defined in Section 7.2.1 - Definition of an Overdose for This Protocol and Reporting of Overdose to the Sponsor, that is not associated with clinical symptoms or abnormal laboratory results.
2. first instance of ALT or AST >500 IU/L from the initiation of study therapy through 14 days following treatment.*
3. first instance of ALT or AST >3x nadir AND >3x Upper Limit of Normal (ULN) from the initiation of study therapy through 14 days following treatment.*

*Note: The purpose of the criteria is to specify a threshold of abnormal hepatic tests that may require an additional evaluation for an underlying etiology. The trial site guidance for assessment and follow up of these criteria can be found in the Investigator Trial File Binder (or equivalent).

Additional events of clinical interest for this trial include:

1. first instance of eGFR < 30 mL/min/1.73 m² from the initiation of study therapy through 14 days following treatment. Creatinine clearance will be evaluated as an estimated GFR (eGFR), based on the MDRD equation:

$$\text{eGFR (mL/min/1.73 m}^2\text{)} = 175 \times (\text{Scr, std})^{-1.154} \times (\text{Age})^{-0.203} \times (0.742 \text{ if female}) \times (1.212 \text{ if black})$$

Scr, std: serum creatinine measured with a standardized assay

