Statistical Methods for Key Safety Analyses	
The All-Subjects-as-Treated population will be employed for safety analyses. The proportion of subjects with adverse experiences of elevated laboratory values that are reported as ECIs described in section 7.2.3.2 during the study therapy period are prespecified as events of clinical interest and will be provided along with the corresponding 95% CIs.
 
In addition, the broad clinical and laboratory AE categories consisting of the percentage of subjects with any AE, a drug related AE, a SAE, an AE which is both drug-related and serious, and who discontinued due to an AE will be summarized in the same manner.

Interim Analyses	
Sentinel cohorts (i.e. first 10 subjects) in each treatment arm for GT1, GT2, GT3, and GT4 subjects will be assessed to determine the treatment duration for the main cohorts (i.e. the remaining subjects still on treatment).

Multiplicity	
No multiplicity adjustment is planned for the study.

Sample Size and Power	
Approximately 250 subjects will be allocated into one of the six treatment arms of combination of MK-3682 (450mg) and MK-8408 (60mg) for 12 weeks with 50 GT1-, 50 GT2-, 50 GT3-, 50 GT4-, 25 GT5- and 25 GT6-infected subjects in Arms 1, 2, 3, 4, 5 and 6, respectively Assuming a protocol violation rate of 10%, the PP population will include approximately 45 subjects in each of Arms 1, 2, 3 and 4. If the SVR₁₂ rate is approximately 96% (43 successes out of 45), the exact 95% CI is (84.9%, 99.5%). The PP population will include approximately 22 subjects in Arms 5 and 6. If the SVR₁₂ rate is approximately 91% (20 successes out of 22), the exact 95% CI is (70.8%, 98.9%). Detailed information is in Section 8.9.1.

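### The one laboratory-specific safety rate with a confidence interval counts reported ECIs rather than measured threshold crossings, so its accuracy depends on complete reporting

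*Combined protocol and SAP*

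**What the plan says.** Section 8.6.2 names six first-tier safety items. The first is "AEs of elevated laboratory values that are reported as ECIs described in Section 7.2.3.2"; the other five are broad AE categories. On method it states: "The 95% CIs for the safety parameters will be estimated using the Clopper-Pearson method". On the time frame: "The primary safety analysis will summarize the safety data for subjects during the treatment period plus 14 days of follow-up".

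The SAP summary in 8.1 describes the same item as "adverse experiences of elevated laboratory values that are reported as ECIs described in section 7.2.3.2 during the study therapy period".

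Table 17 marks this item for a confidence interval. The row "Specific AEs, SOCs or PDLCs" and the row for change from baseline are marked for descriptive statistics only.

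Section 7.2.3.2 lists four laboratory ECIs:

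- ALT or AST above 500 IU/L
- ALT or AST above 3× nadir and above 3× ULN
- "first instance of eGFR < 30 mL/min/1.73" m²
- serum creatinine Grade 2 or higher (above 1.3× ULN) and raised from baseline

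Each runs from the start of study therapy to 14 days after treatment. Each must be reported to the Sponsor within 24 hours, whatever its relationship to study drug.

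No section derives ECI status from the laboratory data or reconciles reported ECIs with it.

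**The concern.** The laboratory ECIs are numeric rules. Section 7.1.5.7 schedules laboratory safety measurements after the first week and then every two weeks on treatment, in order to detect liver and renal signals. Whether a subject crossed a threshold can therefore be read from the data. The endpoint instead counts crossings that were reported as events, so a step between the measurement and the analysis can lose cases. A Clopper-Pearson interval reflects sampling error only and does not widen for events that were never reported.

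No other interval fills the gap. The five broad AE rates include laboratory AEs (Table 17 footnote), but they are not specific to liver or kidney and they depend on reporting too.

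Two wording problems add to this. A fall in eGFR is not an elevated value, although section 4.1.2.1 names the kidney as a potential target organ. And 8.1 uses a shorter window than 8.6.2 and 7.2.3.2.

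**Working it through.** **1. The plan's own interval figures.** Table 20 gives upper limits of the two-sided exact 95% interval. With x events in n subjects, the upper limit is the 0.975 quantile of Beta(x+1, n−x); for x = 0 this is 1 − 0.025^(1/n).

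- 0/25: 1 − 0.025^(1/25) = 13.7% (Table 20: 13.7%)
- 4/50: 19.2% (Table 20: 19.2%)
- 10/250: 7.2% (Table 20: 7.2%)
- 25/250: 14.4% (Table 20: 14.4%)

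All 15 entries reproduce to 0.1 point. The interval arithmetic is sound; the question is what is counted.

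**2. Effect of missed reports.** The documents give neither a true crossing rate nor a reporting rate. Both are assumed here, and the rows show a range.

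| Subjects | True crossings | Reported | Rate | 95% CI |
|---|---|---|---|---|
| 250 | 10 | 10 | 4.0% | 1.9 to 7.2 |
| 250 | 10 | 8 | 3.2% | 1.4 to 6.2 |
| 250 | 10 | 7 | 2.8% | 1.1 to 5.7 |
| 250 | 10 | 5 | 2.0% | 0.7 to 4.6 |
| 250 | 25 | 25 | 10.0% | 6.6 to 14.4 |
| 250 | 25 | 20 | 8.0% | 5.0 to 12.1 |
| 50 | 4 | 4 | 8.0% | 2.2 to 19.2 |
| 50 | 4 | 2 | 4.0% | 0.5 to 13.7 |
| 250 | 1 | 1 | 0.4% | upper 2.2 |
| 250 | 1 | 0 | 0.0% | upper 1.5 |

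Where reported equals true, there is no bias.

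**3. How much the eGFR wording matters.** Inverting the protocol's MDRD equation at eGFR = 30:

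Scr = [30 / (175 × Age^−0.203 × f)]^(−1/1.154), where f is the product of the sex and race factors.

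- Non-black man, 55 years: Scr = 2.28 mg/dL
- Non-black woman, 55 years: Scr = 1.76 mg/dL
- Non-black woman, 85 years: Scr = 1.63 mg/dL (lowest of the cases computed, ages 18 to 85)

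For such a subject to stay within 1.3× ULN, the ULN would have to be at least Scr/1.3 = 1.75, 1.35 and 1.25 mg/dL respectively. The documents give no ULN. If it is 1.0 to 1.2 mg/dL (assumption), 1.3× ULN is at most 1.3 × 1.2 = 1.56 mg/dL, below all three values.

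The creatinine ECI also requires a rise from baseline. Table 8 excludes screening eGFR below 50. Going from 50 to below 30 means creatinine has risen by a factor of more than (50/30)^(1/1.154) = 1.56 since screening, so this condition should be met unless most of the rise came before Day 1. Leaving out eGFR below 30 would therefore change the eGFR component rate but hardly an any-laboratory-ECI composite.

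**4. The windows side by side.** Section 8.1 ends with the therapy period; 7.2.3.2 and 8.6.2 run 14 days longer. The Week 12 visit may be up to 14 days late, so an end-of-treatment sample can fall after the last dose: inside one window and outside the other. The follow-up visit window of −1 to +2 weeks puts the earliest FW4 sample at 4 − 1 = 3 weeks, beyond both windows. The extra 14 days can thus add mainly late Week 12 or unscheduled samples.

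**5. Denominator.** Section 8.5.2 requires a post-dose measurement for the analysis of each laboratory parameter. It does not say whether that applies to this AE-type item. If not, a subject with no post-dose chemistry counts as event-free.

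**The case against.** The strongest reply is that crossing a threshold is itself the ECI, and reporting is mandatory within 24 hours regardless of relatedness. If sites comply, reported ECIs equal crossings. A reader might infer that the rate is biased low. The documents do not support that: they give no under-reporting rate, and over-reporting (reported but not met) would push the other way. This stands. What remains is a dependence that the plan neither removes nor checks.

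A reader might also infer that the running nadir is easily missed at site. Nothing says so. The same criterion is part of two discontinuation scenarios in Table 10, so sites must track it anyway, and site guidance on the ALT/AST criteria is placed in the Investigator Trial File Binder.

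Nor do the documents say that central-laboratory values define the ECIs. Section 7.2.3.2 names no laboratory. The sentence "These samples will be sent to the appropriate central laboratory(ies") belongs to the Day 1 procedures, and pre-dose samples cannot show a post-dose crossing. The point does not need it: 8.6.2 already plans laboratory summaries over time, so measured values will be in the analysis data.

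On eGFR, the item refers to 7.2.3.2 as a whole, which lists eGFR below 30, so inclusion is a fair reading. But a prespecified endpoint should not permit both readings.

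On the window, 8.1 calls itself a summary of the comprehensive plan in the later sections, so 8.6.2 presumably governs. That makes the conflict minor.

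Finally, measured values are already summarised in the second tier, the trial has no formal hypotheses, and no decision threshold hangs on this rate. That limits the consequences. It does not explain why the one laboratory-specific interval should rest on reports when the measurements are available.

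**Conclusion.** The point holds as a weakness in how the endpoint is defined. The only laboratory-specific safety rate with a 95% interval depends on complete reporting of events that could be computed from measured values, and nothing reconciles the two. It can be biased low if crossings go unreported; that it is biased is not shown.

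The size is unknown. Under assumed counts, two unreported crossings out of 10 in 250 subjects move the upper limit from 7.2% to 6.2%, and three move it to 5.7%. In an arm of 50, missing two of four moves it from 19.2% to 13.7%.

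The eGFR gap exists on a literal reading and probably affects only the component rate, if the creatinine ULN is about 1.0 to 1.2 mg/dL. The window conflict is real but minor. The change is worth making because it is cheap and removes the dependence on reporting.

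**What to change.** In 8.6.2, Table 17 and 8.1, define first-tier item (1) from measured results:

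- **Event:** the subject's measured values meet the criterion, given for each of the four laboratory criteria in 7.2.3.2 and for any of them, with eGFR below 30 named explicitly.
- **Denominator:** ASaT subjects with at least one post-dose value.
- **Window:** first dose through treatment plus 14 days, stated identically in all three places.
- **Estimate:** proportion with Clopper-Pearson 95% CI, by arm and combined across genotypes, as now planned.
- **Reconciliation:** a listing of criteria met but not reported as ECIs, and reported as ECIs but not met.

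The cost is one extra derivation from chemistry already scheduled, plus the SAP wording. The reported rate may come out slightly higher. No visit, sample or site reporting duty changes.

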8.6.3 Summaries of Baseline Characteristics, Demographics, and other Analyses

Summaries of demographic and baseline characteristics, pharmacokinetic analyses, analyses of data from the long-term follow-up in this study (as described in Section 7.1.5.6), and analyses for the exploratory endpoints will be described in detail in the supplementary statistical analysis plan (sSAP).

8.7 Interim Analyses

Interim assessments will include the following to evaluate the need to extend the treatment duration from 12 weeks to 16 weeks. If a total of ≥ 3 out of the first 10 subjects in the PP population in a 12-week arm experience virologic relapse by FW4, all subjects already enrolled and on treatment in an 12- week dosing duration arm for that GT will have their treatment duration extended to 16 weeks, and no further subjects will be enrolled.

The probability of observing 3 or more subjects with virologic failure can be computed using the binomial distribution and is a function of the actual total sample size per arm (n) and the assumed proportion of virologic failure ($p = 1 - \text{true SVR rate}$). These probabilities

(expressed as a percent) are displayed in [Table 18](#) for sample sizes (n) of 9 and 10 subjects and true SVR rates of 70, 75, 80, 85, and 90%.

Table 18 Probability of Observing 3 or More Subjects with Virologic Failure

True SVR Rate	Sample Size Per Arm (n)	
	9	10
0.70	53.7%	61.7%
0.75	39.9%	47.4%
0.80	26.2%	32.2%
0.85	14.1%	18.0%
0.90	5.3%	7.0%
0.95	0.8%	1.2%

8.8 Multiplicity

No multiplicity adjustment is planned for the study.

8.9 Sample Size and Power Calculations

8.9.1 Efficacy Analysis

Approximately 250 subjects will be allocated to receive treatment with MK-3682 (450mg) and MK-8408 (60mg) for 12 weeks with a target enrollment of 50 GT1-, 50 GT2-, 50 GT3-, 50 GT4-, 25 GT5- and 25 GT6-infected subjects in Arms 1, 2, 3, 4, 5 and 6, respectively. Assuming a protocol violation rate of 10%, the PP population will include approximately 45 subjects in each of Arms 1, 2, 3 and 4. The PP population will include approximately 22 subjects in Arms 5 and 6.

[Table 19](#) below shows the two-sided 95% CIs for SVR₁₂ under varying assumptions of the number of successes for the PP population. Note that these intervals are not symmetric around the point estimate.

Table 19 Two-Sided 95% Confidence Intervals for SVR₁₂ (PP Population)

Number of subjects in PP population	Observed Number of Successes (%)	Two-Sided 95% Confidence Interval [‡]
22	21 (95.5%)	(77.2, 99.9)
	20 (90.9%)	(70.8, 98.9)
	19 (86.4%)	(65.1, 97.1)
	18 (81.8%)	(59.7, 94.8)
45	43 (95.6%)	(84.9, 99.5)
	41 (91.1%)	(78.8, 97.5)
	39 (86.7%)	(73.2, 94.9)
	37 (82.2%)	(67.9, 92.0)
[‡] Based on the Clopper-Pearson method		

8.9.2 Safety Analysis

The primary safety objective of this study will be assessed by a review of the accumulated safety data. Certain safety endpoints of special interest have been identified in Section 8.4.2.

The ASaT population will include approximately 25 or 50 subjects in each of the 6 treatment arms. When combined across genotypes, the ASaT population will include approximately 250 subjects for combined treatment arm of 12 weeks. The estimate of and the upper bound of the 95% confidence interval for the underlying percentage of subjects with a specific AE given various hypothetical observed number of subjects with that specific AE within the study are provided in Table 20. These calculations are based on the exact binomial method proposed by Clopper and Pearson [49].

Table 20 Estimate of Incidence of a Specific AE and 95% Upper Confidence Bound Based on a Hypothetical Number of Subjects with that Specific AE

n	Hypothetical Number of Subjects with AE	Estimate of Incidence	95% Upper Confidence Bound [†]
25	0	0.0%	13.7%
	2	8.0%	26.0%
	5	20.0%	40.7%
	8	32.0%	53.5%
	10	40.0%	61.3%
50	0	0.0%	7.1%
	2	4.0%	13.7%
	4	8.0%	19.2%
	8	16.0%	29.1%
	10	20.0%	33.7%
250	0	0.0%	1.5%
	10	4.0%	7.2%
	25	10.0%	14.4%
	35	14.0%	18.9%
	50	20.0%	25.5%

[†]Based on the two-tailed exact confidence interval of a binomial proportion (Clopper and Pearson, 1934)

8.10 Subgroup Analyses and Effects of Baseline Factors

To assess the consistency of the response across various subgroups, the SVR₁₂ and SVR₂₄ rate and associated 95% CIs will be estimated within each category of the following baseline factors as classification variables:

- Presence or absence of baseline RAVs to any of the two classes of drugs
- Sex (female, male)
- Age (≥ 65 , < 65)
- Race (White, Black or African American, Asian, Other)
- Ethnicity (Hispanic or Latino, not Hispanic or Latino, Other)
- IL28B genotype (CC vs. non-CC)
- HCV RNA at baseline, $\leq 800,000$ IU/mL versus $> 800,000$ IU/mL; ≤ 2 million IU/mL versus > 2 million IU/mL; ≤ 10 million IU/mL versus > 10 million IU/mL
- Stage of fibrosis (non-cirrhotic, cirrhotic)
- HIV co-infection status (HCV/HIV co-infected, HCV mono-infected)
- Treatment-experienced and treatment-naïve
- For Arm 1: GT1 subjects (GT1a vs. GT1b)

The subgroup analyses will be performed within each treatment arm and based on pooled treatment arm across genotypes, as appropriate.

8.11 Compliance (Medication Adherence)

In this study, as part of the routine recording of the amount of study treatment taken by each subject, the number of tablets remaining in study packaging will be counted, reviewed, and recorded at regular intervals. These results will be used to calculate subject compliance.

A day within the study will be considered an “On-Therapy” day if the subject takes the assigned treatment MK-3682 (450mg) + MK-8408 (60mg) as noted in Section 5.2.

For a subject who is followed for the entire study period, the “Number of Days Should be on Therapy” is the total number of days from allocation to the last scheduled day for treatment administration for that subject. For a subject who discontinued from the study permanently, the “Number of Days Should be on Therapy” is the total number of days from allocation to the date of the last dose of study medication.

For each subject, percent compliance will then be calculated using the following formula:

$$\text{Percent Compliance} = \frac{\text{Number of Days on Therapy}}{\text{Number of Days Should be on Therapy}} \times 100.$$

Summary statistics will be provided on percent compliance by treatment group for the FAS population.

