5.2 Trial Treatment(s)

The treatment to be used in this trial is outlined in [Table 9](#).

Table 9 Trial Treatment for Each Arm

Drug	Dose/Potency	Dose Frequency	Route of Administration	Regimen/Treatment Period	Use
MK-3682	450mg (3 x 150mg tablet)	QD	Oral	12 weeks	Experimental
MK-8408	60mg (6 x 10mg capsule)	QD	Oral	12 weeks	Experimental

The first dose of trial treatment will be administered at the trial site at Visit 2 (Day 1). The doses to be taken at other visits at which a pre-dose PK sample is to be collected will also be administered at the trial site. All other dosing will be performed by the subject (i.e., unsupervised at his/her home) in the morning at approximately the same time each day for MK-3682 and MK-8408.

The investigator shall take responsibility for and shall take all steps to maintain appropriate records and ensure appropriate supply, storage, handling, distribution and usage of trial treatments in accordance with the protocol and any applicable laws and regulations.

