7.1.4 Other Procedures

7.1.4.1 Withdrawal/Discontinuation

Subjects who discontinue/withdraw from treatment prior to completion of the treatment regimen should be encouraged to continue to be followed for all remaining study visits as detailed in Section 7.1.5.4.

When a subject discontinues/withdraws from participation in the trial, all applicable activities scheduled for the final trial visit should be performed at the time of discontinuation. Any adverse events which are present at the time of discontinuation/withdrawal should be followed in accordance with the safety requirements outlined in Section 7.2 - Assessing and Recording Adverse Events.

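### Section 8.11 sets the compliance denominator by study status rather than treatment status, so the same dosing can score about 100% or d/84 within one pooled summary

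*Combined protocol and SAP*

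**What the plan says.** Section 8.11 defines percent compliance as days on therapy over the days the subject should have been on therapy, times 100. A day counts as on therapy "if the subject takes the assigned treatment MK-3682 (450mg) + MK-8408 (60mg) as noted in Section 5.2", so both drugs are needed.

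The denominator has two branches:

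- "For a subject who is followed for the entire study period", it "is the total number of days from allocation to the last scheduled day for treatment administration for that subject".
- Where someone has left the study for good, it "is the total number of days from allocation to the date of the last dose of study medication".

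Results are summarised by treatment group in the FAS, with both branches together. No rule is stated for a subject who stops drug early but remains in follow-up.

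That group exists by design. Most rows of Table 10 (Section 5.8) stop treatment, or allow it to stop, while monitoring continues. Section 7.1.4.1 says that early stoppers "should be encouraged to continue to be followed for all remaining study visits as detailed in Section 7.1.5.4", and Section 7.1.5.4 routes them through an early discontinuation visit into follow-up. One Table 10 row, and withdrawal of consent, end participation in the trial altogether.

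Section 8.11 also says that "the number of tablets remaining in study packaging will be counted, reviewed, and recorded at regular intervals". Table 9 gives the MK-8408 daily dose as "60mg (6 x 10mg capsule").

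**The concern.** The branch is chosen by whether the subject completed the study, which is a different event from completing treatment. Two subjects with identical dosing can therefore receive different compliance values because of something that happens after the last dose. A subject who stops at day 28, attends several follow-up visits and then leaves would fall in the second branch. One who attends every visit would fall in the first.

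Within the second branch the denominator ends at the last dose actually taken. Stopping early cannot reduce the score; only doses missed before the stop can.

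At stake is the meaning of a reported figure. Section 8.5.1 justifies the per-protocol (PP) population as showing efficacy in subjects who took treatment reasonably well, so a reader may turn to the compliance summary for support. That reader would be looking at a mixture of adherence while on drug and persistence with the assigned course, in proportions set by how many early stoppers left the study.

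**Working it through.** Section 8.11 gives a formula but no numerical result, so there is no stated figure to reproduce. The check applies the formula as written.

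**Inputs from the documents.** Planned course 12 weeks = 84 days (Section 5.3); 16 weeks = 112 days if extended (Section 5.12.1); arms of 50 (GT1 to GT4) or 25 (GT5, GT6) (Section 8.9.1).

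**Assumptions.** Stop on day d; no doses missed before the stop; the day of allocation is counted. The documents give no stop day, so a range is shown.

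**Individual scores.** Left the study: d/d. Followed to the end: d/84.

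| Stop day d | Left the study | Stayed in follow-up |
|---|---|---|
| 1 | 1/1 = 100% | 1/84 = 1.2% |
| 14 | 14/14 = 100% | 14/84 = 16.7% |
| 28 | 28/28 = 100% | 28/84 = 33.3% |
| 56 | 56/56 = 100% | 56/84 = 66.7% |
| 77 | 77/77 = 100% | 77/84 = 91.7% |

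Variations on the day-28 case:

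- 112-day course: 28/28 = 100% against 28/112 = 25.0%.
- Doses taken on 25 of the 28 days: 25/28 = 89.3% against 25/84 = 29.8%.
- Allocation day not counted in the denominator: 28/27 = 103.7% against 28/83 = 33.7%. The text does not say which count is meant.

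**Effect of follow-up status alone on an arm mean.** Take 50 subjects, 5 stopping at day 28 and the other 45 fully compliant:

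- All five leave: (45 × 100 + 5 × 100)/50 = 100%.
- All five stay: (45 × 100 + 5 × 33.3)/50 = 93.3%.

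Dosing is the same in both cases. With one stopper in 50 the figures are 100% and 98.7%; with two in 25 they are 100% and 94.7%.

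**Planned mean against the assigned course.** Take 50 subjects with the early stoppers (day 28) all leaving and the others at 98%:

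- Three stoppers, planned: (47 × 98 + 3 × 100)/50 = 98.1%. Assigned course: (47 × 98 + 3 × 33.3)/50 = 94.1%.
- Five stoppers, planned: (45 × 98 + 5 × 100)/50 = 98.2%. Assigned course: (45 × 98 + 5 × 33.3)/50 = 91.5%.

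In both cases the planned mean is slightly above the 98% of those who finished, because each early leaver contributes 100%.

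**The case against.** Several points on the other side have force.

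- **The low score depends on the reading.** The first branch refers to the last scheduled treatment day for that subject. Section 5.8 makes treatment discontinuation permanent, so one can argue that a retained stopper has no scheduled days left. That is possible, but Section 8.11 does not say it. Under that reading every early stopper who missed no dose scores about 100%, and persistence disappears for all of them. The text still has to choose.
- **A reader might infer that the compliance summary will be inflated in general.** The documents do not support that. The effect needs early stoppers who also leave the study, and the protocol steers most of them into follow-up. The completion figures quoted in Section 4.1.2.2.2, from three-drug regimens, are 240 of 240 in Part A and 23 of 24 in Part C, so 3 to 5 leavers per 50 is an illustration and not a forecast.
- **A reader might infer that early stopping is hidden.** It is not. Section 8.12 reports N, mean and range of days on therapy for each drug, so an early stop lowers the mean and can set the minimum. That summary carries no denominator, however, and does not correct the percentage.
- **A reader might infer that MK-8408 capsules go uncounted.** Section 7.1.1.8 has the diary record both tablets and capsules and has sites check it against returned medication. The tablet wording in Section 8.11 is loose, nothing more.
- **Days to last dose is a legitimate measure.** It describes adherence while on drug. Using the assigned course alone would score a stop that Table 10 requires as poor adherence. This stands, and is why one denominator should not simply replace the other.

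**Conclusion.** The inconsistency is real and minor. On the natural reading, and with no doses missed before the stop, a subject who stops on day d of 84 scores about 100% on leaving the study and d/84 on staying. The gap runs from about 99 percentage points (day 1) to about 8 (day 77). The often-quoted kind of contrast, 100% against a third, belongs to a stop near day 28 and is not a general property of the formula. The size of any shift in an arm mean depends on how many subjects stop early, when, and how many leave. The 98.1% against 94.1% rests on assumed values for all three, and with no early leavers the discrepancy from this source is nil.

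It would go too far to infer that efficacy conclusions or the PP population are affected. Section 8.5.1 lists no compliance threshold among the PP violations. Section 8.6.1 handles dropouts through its own missing-data rules. No stopping or extension rule uses percent compliance. What needs correcting is one descriptive statistic.

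**What to change.** Amend Section 8.11, or the supplemental SAP, before database lock:

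1. Apply each denominator to every FAS subject regardless of follow-up status, and report two labelled measures: (a) days on therapy divided by the assigned course (84 days, or 112 if extended); (b) days on therapy divided by days from allocation to last dose, labelled as adherence while on treatment. Measure (a) shows persistence. Measure (b) keeps protocol-directed stops from being read as poor adherence.
2. State that the day of allocation is counted, so that a fully adherent subject scores exactly 100%.
3. Align the pill-count wording with Section 7.1.1.8 so that it covers tablets and capsules. This is wording only.

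No new data or visits are needed: dosing days are in the diary, and Section 7.1.5.4 already collects the last-dose date for those who stop early. The cost is one extra summary line, and the assigned-course figure may look slightly less favourable than the present one.
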